This is an interventional study. Subjects' condition may worsen or improve while undergoing intervention with olanzapine. Participation in this study will not prevent normal clinical care of gastroparesis or its consequences. In addition, some prescribed medications may need to be stopped temporarily during the study. Subjects will also be asked to hold any medications that may potential influence GI motility or appetite within one week prior to starting and for the duration of the study, including prokinetic drugs, macrolide antibiotics (erythromycin), opioid pain medications, GLP-1 mimetics. If subjects are taking any of these medications, their symptoms may return or worsen when they are stopped. However, the stopping of medications is temporary and is not felt to cause any undue hardship. Finally, there is a risk that some of the questions in the surveys may produce emotional distress. If the subject desires, he/she can be referred to a mental health specialist within the UMHS or another provider outside the UMHS system.

4 ELIGIBILITY CRITERIA

Inclusion Criteria:

- Male or female between 18 and 80 years of age, inclusive.
- Has gastroparesis at screening (gastric half-time of emptying > upper limit of normal as determined by wireless motility capsule)
- Must have a > or = 6 month history of relevant symptoms of gastroparesis, (e.g., chronic post-prandial fullness, early satiety, postprandial nausea), patients will have a mean of the daily scores over a minimum of 7 days indicating > or = mild (2) assessed using the GCSI-DD during the screening period prior to randomization.
- A female subject is eligible to participate if she is of non-childbearing potential or child-bearing potential and agrees to use one of the approved contraception methods. Female patients must agree to use contraception for at least 5 days following the last dose of study medication.

- Male subject must agree to use of contraception. Contraception must be followed from the time of the first dose of study medication through at least 5 days after the last dose of study medication.
- BMI \geq 18 and < 30 kg/m2 (inclusive).
- Subjects on anti-hypertensive medications may be allowed to participate but should exercise caution given risk of orthostatic hypotension
- Subject has never had a gastrectomy, nor major gastric surgical procedure or any evidence of bowel obstruction or strictures within the previous 12 months
- Dosage of any concomitant medications has been stable for at least 3 weeks.
- Estimated (or measured) glomerular filtration rate \geq 30 mL/min.
- QTcB or QTcF < 450 msec or QTc < 480 msec in patients with Bundle Branch Block based on single or average QTc value of triplicate values obtained over a brief recording period.
- Capable of giving written informed consent, which includes compliance with the requirements and restrictions listed in the consent form.
- AST and ALT < 2xULN; alkaline phosphatase and bilirubin ≤ 1.5xULN; normal CBC, TSH, and prolactin levels.

Exclusion Criteria:

- Subject has a history of diabetes mellitus, hyperglycemia, hyperlipidemia, cardiovascular disease, cerebrovascular disease, seizures, hyperprolactinemia, Parkinson's disease, or dementia.
- Subject has a history of elevated glucose level (fasting blood glucose level of 100-126 mg/dl and/or non-fasting glucose level of 140-200 mg/dl)
- Subject has history of underlying schizophrenia, bipolar disorder, suicidal ideation/attempt, or has used olanzapine in the past.
- Subjects with a pacemaker and/or defibrillator
- Subject has acute severe gastroenteritis
- Subject has a gastric pacemaker
- Previous gastric surgeries
- Subject is on chronic enteral (e.g., feeding tube) or parenteral feeding
- Subject has pronounced dehydration
- Subject has evidence of severe cardiovascular autonomic neuropathy (e.g. history of recurrent syncope in the last 6 months)
- Subject has a history of eating disorders (anorexia nervosa, binge eating, bulimia)
- Use of medications potentially influencing upper gastrointestinal motility or appetite within one week of the study (e.g., prokinetic drugs, macrolide antibiotics (erythromycin), GLP-1 mimetics)
- Regular opiate use
- Subjects who are taking drugs that potentially interact with olanzapine including diazepam, lorazepam, alcohol, carbamazepine, fluvoxamine, olanzapine and

fluoxetine in combination, CNS acting drugs, levodopa and dopamine agonist, and olanzapine when used in combination with lithium or valproate

- History or presence of clinically significant gastro-intestinal, hepatic or renal disease or other condition that would in the opinion of the investigator or medical monitor make the subject unsuitable for inclusion in this clinical study.
- The subject has participated in a clinical trial and has received an investigational product within the following time period prior to the first dosing day in the current study: 30 days, 5 half-lives or twice the duration of the biological effect of the investigational product (whichever is longer).
- History of sensitivity to any of the study medications, or components thereof or a history of drug or other allergy that, in the opinion of the investigator would make the subject unsuitable for inclusion in this clinical study
- Where participation in the study would result in donation of blood or blood products in excess of 500 mL within a 56 day time-period.
- Pregnant females as determined by positive serum or urine hCG test (from the first urine of the day) at screening or prior to dosing.
- Lactating females.
- Current or chronic history of liver disease, or known hepatic or biliary abnormalities (with the exception of Gilbert's syndrome or asymptomatic gallstones).
- Subject has a history of dysphagia.
- Subject has had intrapyloric botox injections within the past 6 months.

5 SUBJECT ENROLLMENT

Most patients with gastroparesis are seen in gastroenterology or general medicine clinics. Patients will be recruited from gastroenterology and general medicine clinics at Taubman Center and in the satellite clinics within the University of Michigan Health System. Eligible subjects will be contacted and given material explaining the nature of the study, including information related to wireless motility testing and introduction to olanzapine. They will be given time to read the materials. If they choose to participate, they will sign the consent document in the presence of the PI and/or Designee. Subjects will be enrolled on a first come, first served basis. This approach will ensure that subjects are representative of the population of patients with gastroparesis in Southeast Michigan.

Emails to providers in the General Medicine and Gastroenterology clinics in the University of Michigan System, public advertisements, and telephone calls will be utilized to recruit subjects.

Subjects who do not meet inclusion/exclusion criteria will not be enrolled in the study. All data collected from subjects who are screen failures will be saved for data analysis.

6 STUDY DESIGN AND PROCEDURES

This is a pilot study of 10 consecutive subjects ages 18 – 80 with documented delayed gastric emptying within the past 2 years and history of nausea, vomiting, bloating, anorexia, early satiation, post-prandial fullness, and weight loss for at least 6 months without structural or organic cause will be enrolled. This will be an open label trial without a placebo arm to determine efficacy and safety of the medication in this population. This will be a single center study with subjects being enrolled at the University of Michigan. [name] at Massachusetts General Hospital will act as a co-I and will assist with data analysis but will not enroll any patients. [name] will receive only de-identified information.

The study will consist of a screening/baseline period of up to 30 days, an 8-week treatment period, and a 14-day post treatment safety follow-up visit and assessment of symptoms.

Screening/Baseline:

Subjects will participate in a screening/baseline visit within 30 days prior to study dosing. Subjects will be instructed to fast prior to the screening visit at which time they will undergo blood sampling for complete blood count (CBC), complete metabolic panel (CMP), lipid profile, insulin, Hgb A1c, prolactin, TSH, and urine or blood pregnancy screen (if applicable). A baseline ECG will also be performed. Ghrelin levels will be measured. Baseline vital signs, height, weight, and BMI will also be calculated. They will also have their gastric emptying assessed by wireless motility capsule (WMC). To be eligible for the study, the subjects' gastric emptying time, as determined by WMC, needs to be greater than 5 hours. Potential subjects will complete the gastroparesis cardinal symptom index daily diary (GCSI-DD) evaluation, appetite visual analog score (VAS), and Bristol Stool Form Scale (BSFS) for a minimum of 7 days to determine baseline level of symptoms [41]. Questionnaires will be completed in the evening after dinner. Mean total GCSI-DD score must be ≥ 2 in order to qualify for the study.

Week 1 – Week 8:

Subjects will initially start on olanzapine 2.5 mg by mouth daily to be taken at bedtime. Subjects will return on days 7 and 14 to determine response to medication. Medication dose can be increased to 5 mg on day 7 and 10 mg on day 14, respectively, based on incomplete symptom response, which is defined as a mean change in GCSI-DD score < 0.5 from baseline. Height and weight will be measured on Day 7. The total dose of olanzapine will not exceed 10 mg daily during this study. Subjects will be monitored for adverse events and undergo blood sampling for glucose, insulin, and Hgb A1c on day 14. Vital signs, height, weight, and BMI will also be evaluated. Subjects will be instructed to bring their study medication with them on day 14 for assessment of study drug accountability.

Subjects will be contacted by phone at least once within 2 weeks following the day 14 visit to assess for potential side effects. Subjects may also come in for an extra/optional study visit between the Day 14 and Day 35 visits, if warranted by side effects.

Subjects will return on day 35 to monitor for adverse events, vital signs, height, weight, BMI, and glucose check.

During the study, subjects will rate their gastroparesis symptoms on a daily basis by completing the GCSI-DD and appetite VAS questionnaires. Subjects will also record daily the number of stools and their consistency [42]. Subjects will be asked to complete all diaries after the evening meal. The subjects will fast prior to returning to clinic on the morning of day 56 to undergo assessment of their gastric emptying time by WMC and complete an appetite VAS. Blood sampling for LFTs, glucose, insulin, Hgb A1c, and ghrelin levels will be performed. Vital signs, height, weight, and BMI will also be measured. All remaining study medication will be returned to the clinical unit for final drug accountability. Subjects will continue to rate their gastroparesis symptoms for 14 days following the end of dosing.

Adverse events, vital signs, and laboratory parameters will be assessed to monitor overall safety and tolerability of the medication. Common potential adverse effects of the medication include orthostatic hypotension, weight gain, hyperglycemia, hyperlipidemia, increased prolactin level, akathisia, somnolence, and tremor. Serious adverse effects include sudden cardiac death, diabetic coma, venous thromboembolism, cerebrovascular disease, seizure, and suicidal intent. A subject will be withdrawn from the study if they experience any serious adverse events or if they develop hyperglycemia (fasting glucose level > 150 mg/dl or non-fasting glucose level > 180 mg/dl), or weight gain (\geq 5 kg/wk). The FDA definition for serious adverse events (SAE) will be used which is defined as an AE resulting in any of the following outcomes: Death, a life-threatening adverse event, inpatient hospitalization or prolongation of existing hospitalization, a persistent or significant incapacity or substantial disruption of the ability to conduct normal life functions, or a congenital anomaly/birth defect related to the adverse event. Important medical events that may not result in death, be lifethreatening, or require hospitalization may be considered serious when, based upon appropriate medical judgment, they may jeopardize the patient or subject and may

require medical or surgical intervention to prevent one of the outcomes listed in this definition. The PI will determine whether the SAE is related or possibly related to the drug. The trial will stop if any SAE related to the drug is encountered. Subjects will be allowed to use ondansetron, promethazine, and/or prochlorperazine as rescue medications during the study. Laxatives, including Miralax, magnesium, Dulcolax, stool softeners, fiber supplements, and/or linaclotide may also be used during the study to treat underlying constipation. Subjects will not be allowed to use any prokinetic agents, such as Reglan, domperidone, or macrolide antibiotics (e.g. erythromycin) during the study. Rescue and concomitant medications (prescriptions or OTC medications) ongoing at the Screening Visit and/or started from the Screening Visit onwards until the last study related activity will be documented in the Prior and Concomitant Medication and Rescue medication pages of the Case Report Form (CRF). Subjects will be asked to monitor and record usage and frequency of rescue medications and laxatives used during the study.

Post-Treatment Assessment:

At the conclusion of 56 days of dosing, subjects will return for a follow-up visit 14 days (+ 2 days) after the last dose of study medication. All subjects will have blood sampling for CBC, CMP, lipid profile, TSH, prolactin, insulin, Hgb A1c, and ghrelin. Height, weight, and BMI will be calculated. One final appetite VAS will be completed. The duration of each patient's participation in the study from screening to follow-up visit will be approximately 14 weeks.

Subjects are free to discontinue participation in the study at any point. If a subject decides to prematurely discontinue from the study, they will be contacted within two weeks for safety follow-up visit(s). Reasons for withdrawal will be documented by the PI. If the reason for removal of a subject from the study is an AE, the principal specific event will be recorded on the CRF. The subject will be followed until the AE is resolved.

Gastric Motility:

Gastric motility will be tested by using the WMC wireless capsule system (The SmartPill Corporation, Buffalo, NY). This offers a potentially more complete examination into possible etiologies for gastroparesis including delayed gastric emptying as well as gastric and small bowel contractility abnormalities. We will follow the protocol for measuring gastric emptying by wireless motility capsule as described previously in the literature [43]. Gastric emptying time (GET) is defined as the duration of time from capsule ingestion to entry of the capsule into the duodenum. Subjects will swallow the WMC capsule with 50 ml of water followed by ingestion of a standardized meal comprising of a nutrient bar, which has a total caloric value of 255 kcal (72%)

carbohydrate, 24% protein, 2% fat, and 2% fiber) [44]. Because of the low risk of capsule retention especially once the capsule enters the colon, plain abdominal radiograph (KUB) will be performed only if there is no documentation of the capsule passing the ileocecal valve and the patient has symptoms of capsule retention. Pressure data recorded by the WMC capsule will be analyzed for 1 hour before and after the WMC empties the stomach (GET). The analyzed parameters are: number of contractions (Ct), and motility index defined as: MI = Ln (sum of pressure amplitudes * number of contractions +1) [45].

Stopping Criteria:

The purpose of this study is to ensure that severe complications to olanzapine in gastroparesis are rare and to see whether olanzapine might improve symptoms in gastroparesis. We will treat ten patients with gastroparesis. The trial will stop if any SAE related to the drug is encountered.

Study Timeline:

Figure 1 Gastroparesis Subject Timeline

7 Data Collection and Management Procedures

Data Handling and Entry: All data including questionnaire results and physiologic testing will be recorded and reviewed by the study team. Data will then be entered into an electronic case report form (eCRF) that complies with Title 21 of the Code of Federal Regulations (21 CFR Part 11). All passwords will be strictly confidential to protect subject's protected health information (PHI). Only the Primary Investigator (PI) and Study Coordinator will have access to the data and subject identifiers. Only the PI and Study Coordinator will be allowed to enter data onto the password-protected web-based server.

Computer Systems: Data entry will be entered into REDCAP which is validated and conforms to regulatory requirements. Only the Primary Investigator (PI) and Study Coordinator will have access to the data and subject identifiers. Only the PI and Study Coordinator will be allowed to enter data onto the password-protected web-based server.

Data Validation: Validation checks will be programmed within the eCRF system as well as supplemental validation performed by review of the downloaded data, will be applied to the data in order to ensure accurate, consistent, and reliable data.

Direct Access to Source Data: A developed review procedures that complies with Good Clinical Practice (GCP) guidelines.

Source Document/Case Report Form Completion: Source documents and the eCRFs will be completed for each study patient. It is the Investigator's responsibility to ensure the accuracy, completeness, and timeliness of the data reported in the patient's source document/eCRF. The source document/eCRF should indicate the patient's participation in the study and should document the dates and details of the study procedures, AEs, and patient status.

Record Retention: The Investigator will maintain all study records according to applicable regulatory requirement(s).

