Olanzapine is a second generation anti-psychotic that is FDA approved for the treatment of schizophrenia and bipolar disorder. Second generation anti-psychotics typically have fewer extrapyramidal side effects (e.g. akathisia, dystonia, parkinsonian symptoms) as well as tardive dyskinesia compared to older anti-psychotics [9, 10]. However, they do carry potential for serious metabolic risk, specifically weight gain, hypertension, hyperlipidemia, and ultimately development of diabetes mellitus. Olanzapine has been associated with one of the highest risks of weight gain among atypical anti-psychotics [11, 12]. It is unclear if this is related to other actions or if it is related to attenuation of the disease process. Patients with schizophrenia may have a predisposition towards obesity with a prevalence of up to twice the general population [13]. Genetic predisposition, higher prevalence of smoking, and neuroendocrine changes associated with psychosis have all been postulated as possible contributing factors to increased obesity in schizophrenia and bipolar disorder [14-18].

Olanzapine may also have other therapeutic effects outside of controlling psychosis. Phase I and II studies have shown olanzapine significantly relieves nausea and emesis in a palliative care setting [19-21]. It was found to be safe in both trials and helped stimulate appetite and augment weight gain. There is also evidence that olanzapine may be beneficial in the

treatment of eating disorders. Several double blind, placebo-controlled trials have shown benefit of olanzapine in terms of attaining goal BMI and improving psychological measures [22-24]. Furthermore, the medication was well tolerated in this population without development of adverse metabolic events [22, 23, 25].

Olanzapine has actions at multiple receptors throughout the body, which may make it a unique drug for the treatment of gastroparesis. These include antagonism of dopamine, serotonin, $alpha_1$ adrenergic, muscarinic, and histamine receptors [26, 27]. Many of these receptors, especially D₂ and 5HT₃, are involved in the signaling of nausea and emesis [28]. As a result, olanzapine may have anti-nausea properties that could be utilized in gastroparesis. Antagonism of D₂ receptors may also provide motor effects in the stomach, as this is one of the main mechanisms of action for metoclopramide [29-31].

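### Weight and BMI change is measured from a visit up to 30 days before the first dose, so it mixes pre-dose drift with drug effect and may misstate olanzapine weight gain

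*Combined protocol and SAP*

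**What the plan says.** All references are to the combined protocol and SAP.

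- Section 6, Screening/Baseline: "Subjects will participate in a screening/baseline visit within 30 days prior to study dosing". Among the procedures listed for that visit: "Baseline vital signs, height, weight, and BMI will also be calculated". The symptom diary is also kept "for a minimum of 7 days to determine baseline level of symptoms", and eligibility depends on it.
- Section 6, Week 1 – Week 8, opens with dosing: "Subjects will initially start on olanzapine 2.5 mg by mouth daily to be taken at bedtime". The text describes no visit on the day of the first dose and no weight at that point.
- The first weight after screening: "Height and weight will be measured on Day 7". Weight is measured again on Day 14, on Day 35 ("Subjects will return on day 35 to monitor for adverse events, vital signs, height, weight, BMI, and glucose check"), on Day 56 and at the post-treatment visit.
- Section 6 describes an open-label trial with no placebo arm. Section 10 examines change from baseline with paired tests, and adds a hierarchical regression over all measurement times.
- Section 1 on the drug: "Olanzapine has been associated with one of the highest risks of weight gain among atypical anti-psychotics". Section 2 names BMI among the Aim 1 safety measures, and section 3 lists weight gain first among the drug's risks.

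**The concern.** A single-arm study attributes change from baseline to the drug, so the baseline should sit as close to the first dose as possible. Here the baseline weight may be a month old when dosing starts. Whatever happens to weight in that month is added to, or subtracted from, the change reported for olanzapine.

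Two statements in the protocol make loss before dosing plausible. The study population in section 6 has a history that includes "early satiation, post-prandial fullness, and weight loss for at least 6 months". Section 3 has drugs affecting motility or appetite held from about a week before the start, and warns that symptoms may come back or get worse. A baseline weight taken before that hold would not reflect it.

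At stake is the estimate of a named safety measure for a drug whose weight effect the protocol itself stresses. Section 1 says the pilot's efficacy and safety findings could be used in a larger randomised trial, so a distorted estimate could carry forward.

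**Working it through.** The plan states no expected change, SD, power or drift rate for weight, so there is no figure of its own to reproduce. The check asks how much drift the schedule can let in.

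**Inputs from the documents**
- Gap from screening to first dose: at most 30 days (section 6). If the diary starts at the screening visit, at least about 7 days; that start point is an inference.
- First on-drug weight: Day 7.
- Sample size: 10.

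**Assumed inputs**
- Mean pre-dose loss: 0, 0.25 or 0.5 kg/week.
- SD of weight change between subjects: 2 to 3 kg.

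**Step 1. Interval from baseline weight to first on-drug weight.** At most 30 + 7 = 37 days, of which 7 are on drug. At the 7-day gap, 7 + 7 = 14 days.

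**Step 2. Bias.** Observed change = on-drug change − (loss rate × gap in days / 7).

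| Assumed loss before dosing | 7-day gap | 30-day gap |
|---|---|---|
| 0 kg/week | 0 kg | 0 kg |
| 0.25 kg/week | 0.25 × 7/7 = 0.25 kg | 0.25 × 30/7 = 1.07 kg |
| 0.5 kg/week | 0.5 × 7/7 = 0.50 kg | 0.5 × 30/7 = 2.14 kg |

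A gain before dosing gives the same sizes with the opposite sign, and weight gain on drug is then overstated. For the group mean, the gap that matters is the average over subjects, not the maximum allowed.

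**Step 3. Scale.** The 95% half-width for a mean change is t(0.975, 9)/√10 × SD = 0.715 × SD. For an SD of 2 kg this is 1.4 kg; for 3 kg it is 2.1 kg. Of the cells above, only 0.5 kg/week over 30 days reaches that range. At 0.25 kg/week the bias stays below even the smaller half-width across the whole window, since 1.07 < 1.4.

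**Step 4. Illustration.** Suppose the true 8-week gain is 3 kg (assumed).
- At 0.25 kg/week loss, the observed gain is 3 − 0.25 = 2.75 kg (7-day gap) or 3 − 1.07 = 1.93 kg (30-day gap).
- At 0.5 kg/week, it is 3 − 0.50 = 2.50 kg or 3 − 2.14 = 0.86 kg.

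**Step 5. Can the planned analysis remove it?** Change from Day 7 to Day 56 does not use the screening weight and covers 49 of 56 treatment days, so it is free of pre-dose drift. It omits the first week on drug. The hierarchical regression uses every weight, but none marks the start of dosing. It therefore cannot split the screening-to-Day-7 change into drift and first-week drug effect.

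**Step 6. With a weight at first dose.** The gap becomes 0 and the first interval 7 days. The bias in Step 2 is 0 kg at any drift rate and in either direction.

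**The case against.** A reader might infer that the plan definitely understates weight gain. The documents do not support that. They give neither a rate nor a direction of weight change before dosing. Weight loss is one item in a descriptive history, not an entry criterion in section 4, and past loss does not establish continuing loss. Section 4 also requires stable doses of concomitant drugs for at least 3 weeks and a BMI of at least 18, and excludes pronounced dehydration and chronic tube or parenteral feeding.

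The medication hold is weak evidence of a month of drift. It lasts about a week before dosing and applies only to subjects on those drugs, and the warning in section 3 concerns symptoms, not weight. The matching exclusion in section 4 can be read as placing the hold before study entry, in which case it precedes the baseline weight.

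A second tempting inference is that drift and drug effect can never be told apart. That is too strong: later on-drug change is clean, and the week it misses is spent on the starting dose. Weight gain is also listed in section 6 as a potential adverse effect, and adverse events are recorded whatever the baseline.

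A third is that no first-dose weight exists. The subject timeline (Figure 1) cannot be read here, and section 4 mentions a pregnancy test at screening or before dosing, which is compatible with a pre-dose contact.

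Finally, this is a 10-subject pilot sized on symptoms and appetite, and the protocol treats weight gain partly as a possible benefit.

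All of this limits the certainty, direction and size of the bias. What remains is that the change measured from screening includes up to 30 days off drug, with nothing in the readable text to take it out. Treating weight gain as a possible benefit does not help, because the estimate is then misstated for that purpose too.

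**Conclusion.** The concern holds as a possible misstatement of unknown sign. In the readable text, weight and BMI change from baseline combines drift before dosing with the effect of olanzapine. Loss before dosing is plausible and would lead to understatement, but it is not documented.

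If the assumed loss rates apply, the effect is small at a one-week gap (at most 0.50 kg). At the full 30 days it is between 1.07 and 2.14 kg for the two non-zero rates. The upper figure needs the highest assumed rate together with the longest gap as the average over all subjects, and should not be quoted as the expected bias. Where bias is present, the confidence interval does not reflect it, because it shifts the mean.

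The conclusion on size rests on the assumed drift rates, the assumed SD and the inferred 7-day minimum. The conclusion on structure rests only on the visit schedule, the change-from-baseline analysis and the lack of a control arm, subject to what the timeline figure shows.

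**What to change.** Record weight when the first dose is supplied, and name it in sections 6 and 10 as the baseline for all weight and BMI change. If the timeline figure already shows such a weight, state it in the text and name it as the baseline. Keep the screening weight for the BMI entry criterion, and report the change from screening to first dose separately as off-drug drift.

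The cost is one extra weight, a short wording change, and possibly a brief in-person contact at first dispensing. Eligibility depends on diary and capsule results that may become available only after the screening visit, so a later contact to supply drug may be needed anyway.

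The change removes drift before dosing only. Any weight trend during treatment that is unrelated to olanzapine, including one caused by the continuing medication hold, remains unseparated in a single-arm design.
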